# 1 SYNOPSIS

| Title: A Randomized, Double-Blind, Double-Dummy, Active Controlled Study to Evaluate the Safety, Tolerability, Pharmacokinetics, and Efficacy of ABBV-3373 in Subjects with Moderate to Severe Rheumatoid Arthritis |  |
|---|--|
| Background and Rationale:  | 
Tumor necrosis factor (TNF)<math>\alpha</math> antagonists are considered effective therapies with established safety profiles in patients with immune-mediated inflammatory diseases, including rheumatoid arthritis (RA). Nevertheless, TNF<math>\alpha</math> antagonists as well as other biologics and targeted synthetic disease-modifying antirheumatic drugs (DMARDs) provide 50% improvement in arthritis scores (ACR50) for fewer than half of RA subjects, even in combination with methotrexate (MTX), indicating that there remains an unmet clinical need for improved therapies.
 
Glucocorticoid receptor modulators (GRMs) are potent drugs for treating many inflammatory diseases, including RA. However, the full efficacy of GRM therapy is not achieved with existing agents due to systemic side effects.
 
ABBV-3373 is an antibody-drug conjugate (ADC) composed of adalimumab (the active component of Humira®) conjugated to A-1677770, a proprietary, highly potent GRM (also referred to as the payload) being developed for the treatment of immune-mediated inflammatory diseases including RA. This adalimumab/GRM ADC has the potential to deliver a highly potent anti-inflammatory payload selectively to the activated immune cells that express transmembrane TNF, and meanwhile to minimize systemic exposure to the free payload GRM. Therefore, the adalimumab/GRM ADC is a promising novel therapeutic agent which can achieve transformational efficacy relative to adalimumab while reducing side effects caused by free GRM systemic exposure.
 |
| Objective(s) and Endpoint(s):  | 
Primary
 
 
To assess the safety, tolerability, and efficacy of ABBV-3373 administered every other week (eow) intravenously (IV) in subjects with moderately to severely active RA on background MTX.
 
To compare clinical efficacy of ABBV-3373 with adalimumab and to test the concept that an anti-TNF antibody-drug-conjugate has the potential to provide superior efficacy than the traditional anti-TNF antibody in RA.
 
 
Secondary
 
 
To compare adalimumab with synthetic placebo control to establish assay sensitivity.
 
To assess the pharmacokinetics (PK), pharmacodynamics and immunogenicity of ABBV-3373.
 
To assess the durability of the treatment effect of ABBV-3373 after discontinuation.
 
  |

|  |  |
|--|--|
|  | 
Primary Endpoint:
The change in disease activity score (DAS)28 (C-reactive protein [CRP]) from Baseline (BL) at Week 12.
  |
| Investigator(s):  | Multi-center.  |
| Study Site(s):  | Approximately 40 sites; United States, Puerto Rico, Germany, Hungary, Israel, Netherlands, Poland.   |
| Study Population and Number of Subjects to be Enrolled: | The study population consists of adults with moderate to severe RA. Approximately 45 subjects will be enrolled.  |
| Investigational Plan:                                   | 
This is a randomized, double-blind, double-dummy, adalimumab active-controlled (12-week) Phase 2a study to assess the safety, tolerability, PK, pharmacodynamics, immunogenicity and efficacy following multiple IV administrations of ABBV-3373 or multiple subcutaneous (SC) injections of adalimumab in subjects with RA on background MTX. In the actively controlled period of the first 12 weeks of treatment, 45 subjects will receive either ABBV-3373 100 mg IV and the matching placebo for adalimumab SC eow or in the control arm the matching placebo for ABBV-3373 IV and adalimumab 80 mg SC eow (double-dummy) according to a 2:1 ratio. Thereafter, all subjects enter a 12-week double-blind extension period. At Week 12, the administration of ABBV-3373 will stop (i.e., the last dose of ABBV-3373 will be given at Week 10) to assess the durability of the observed clinical effects up to 24 weeks. To keep blinding of the study beyond Week 12, the subjects randomized to ABBV-3373 will receive placebo injections, whereas subjects randomized into the adalimumab arm will continue their 80 mg dosing until Week 22. At Week 12 and within the blinded extension period subjects who have not achieved at least a 20% improvement in both their swollen joint count and tender joint count based on 28 joint assessment compared with BL may be discontinued from the study at the discretion of the Investigator. Subsequently, standard of care may be administered at the discretion of the Investigator.
 
After all endpoints are assessed at Week 24, a telephone contact is planned to follow up on safety 70 days after the last dose.
 |
| Key Eligibility Criteria:                               | 
 
• Subjects or their legally authorized representative must voluntarily sign and date an informed consent, approved by an independent ethics committee (IEC)/institutional review board (IRB), prior to the initiation of any screening or study-specific procedures.
 
• Adult male or female, between 18 and 75 years of age inclusive at Screening.
 
• Diagnosis of RA for > 3 months based on the 1987 ACR classification criteria or 2010 ACR/European League against Rheumatism (EULAR) criteria.
 
• Subject meets the following disease activity criteria: <math>\geq 4</math> swollen joints (based on 28 joint count) and <math>\geq 4</math> tender joints (based on 28 joint count) at Screening and BL Visits; and DAS28(CRP) <math>\geq 3.2</math> at Screening.
 
   |

|  |   |
|--|---|
|  | 
 
Incomplete response to MTX. Subjects must have been on oral or parenteral MTX therapy <math>\geq 3</math> months and on a stable prescription of 15 to 25 mg/week (or <math>\geq 10</math> mg/week in subjects intolerant of MTX at doses <math>\geq 15</math> mg/week) for <math>\geq 4</math> weeks prior to the first dose of study drug. Subject must be expected to be able to continue on stable dose of MTX for the duration of study participation.
 
                     |
| Study Drug and Duration of Treatment: | 
ABBV-3373 (50 mg/mL) and matching placebo, adalimumab (80 mg/0.8 mL) and matching placebo.
 
In the first 12 weeks of treatment, subjects will receive either ABBV-3373 100 mg IV and the matching placebo for adalimumab SC eow or in the control arm the matching placebo for ABBV-3373 IV and adalimumab 80 mg SC eow. At Week 12, the administration of ABBV-3373 will stop (i.e., the last dose of ABBV-3373 will be given at Week 10) to assess the durability of the observed clinical effects up to 24 weeks.
 |
| Date of Protocol Synopsis:            | 04 September 2020   |

## 2 INTRODUCTION

### 2.1 Background and Rationale

---

#### Why Is This Study Being Conducted

Tumor necrosis factor (TNF) $\alpha$  antagonists reduce the signs and symptoms of disease by reducing inflammation and limiting the progression of tissue destruction and are considered effective therapies with established safety profiles in patients with immune-mediated inflammatory diseases, including rheumatoid arthritis (RA). Nevertheless, TNF $\alpha$  antagonists as well as other biologics and targeted synthetic disease-modifying antirheumatic drugs (DMARDs) provide 50% improvement in arthritis scores (American College of Rheumatology 50% improvement criteria [ACR50]) for fewer than half of RA subjects, even in combination with methotrexate (MTX), indicating that there remains an unmet clinical need for improved therapies.

Glucocorticoid receptor modulators (GRMs) are potent drugs for treating many inflammatory diseases. In RA, GRMs such as prednisone are highly effective at reducing inflammation and fatigue as well as relieving pain. However, the administration of GRMs is limited due to their side effect profile including (but not limited to) hypothalamic-pituitary-adrenal (HPA) axis suppression, increased rates of bone fracture due to osteoporosis, hyperglycemia, glaucoma, skin thinning and weight gain. Thus, the full efficacy of GRM therapy is not achieved with existing agents due to systemic side effects.

ABBV-3373 is an antibody-drug conjugate (ADC) composed of adalimumab (the active component of Humira®) conjugated to A-1677770, a proprietary, highly potent GRM (also referred to as the payload) being developed for the treatment of immune-mediated inflammatory diseases including RA. This adalimumab/GRM ADC has the potential to deliver a highly potent anti-inflammatory payload selectively to the activated immune cells that express transmembrane TNF, and meanwhile to minimize systemic exposure to the free payload GRM. Therefore, the adalimumab/GRM ADC is promising as a novel therapeutic agent which can achieve transformational efficacy relative to adalimumab while reducing side effects caused by free GRM systemic exposure.

#### Clinical Hypothesis

ABBV-3373 is safe and well-tolerated and provides superior efficacy in subjects with moderately to severely active RA on background MTX compared to adalimumab.

### 2.2 Benefits and Risks to Subjects

---

The clinical efficacy of TNF inhibitors and GRMs in the treatment of RA is well established. Based on the preclinical data discussed in the ABBV-3373 Investigator's Brochure, ABBV-3373 is expected to demonstrate therapeutic benefit in treatment of RA and other immune-mediated inflammatory diseases with a favorable safety profile. Preclinical toxicology of ABBV-3373 suggests that the potential risks to human subjects receiving ABBV-3373 treatment are consistent with known effects of adalimumab and glucocorticoids (GCs). ABBV-3373 was tested in a Phase 1 single ascending dose (SAD) study in healthy volunteers in which 6 cohorts of subcutaneous (SC) (30, 100, 300 mg) and intravenous (IV) (30, 300, 900 mg) successfully completed dosing.

Medical review of the available safety data from the Phase 1 study did not identify any unexpected risk or trend to the healthy volunteer population. All single doses tested to date have been well tolerated. For further details, please see the-ABBV-3373 Investigator's Brochure.

In clinical settings, TNF antagonists and GCs have been associated with an increased risk of serious infections due to bacterial, mycobacterial, invasive fungal, viral, parasitic, or other opportunistic pathogens. Opportunistic infections have included tuberculosis (TB) and histoplasmosis. Patients will be closely monitored during the clinical study for any signs of infection.

Tumor necrosis factor antagonists have also been associated with an increased risk for malignancy (including lymphoma), hepatitis B virus (HBV) reactivation, worsening or new onset heart failure, and rarely central nervous system demyelinating disease, pancytopenia including aplastic anemia, and lupus-like syndrome.

The risk of hypersensitivity reaction or other post-dose systemic reaction for humans who receive multiple doses of ABBV-3373 is considered a potential risk. During Study M16-560, 1 case of anaphylactic shock was observed following repeated eow IV (over 3 minute bolus injection) administration of ABBV-3373. The event was assessed by the investigator and AbbVie to be reasonably related to study drug. The administration of biologics may lead to such reactions; therefore, patients will be closely monitored during and post drug administrations.

Hypertension is one of the most commonly reported events for GCs in patients, especially with high doses of GCs. Therefore, blood pressure and other vital signs will be monitored during the trial.

Based on the above considerations, the risk to RA patients receiving multiple doses of ABBV-3373 is considered manageable and acceptable. In addition, based on the population and disease being studied and the anticipation that COVID-19 related risks are not expected to differ substantially between study subjects and the broader population of subjects receiving treatment for RA, no change to the benefit/risk balance for subjects in this study is expected.

## 3 STUDY OBJECTIVES AND ENDPOINTS

### 3.1 Objectives

---

#### Primary

1. To assess the safety, tolerability, and efficacy of ABBV-3373 administered every other week (eow) intravenously (IV) in subjects with moderately to severely active RA on background MTX.
2. To compare clinical efficacy of ABBV-3373 with adalimumab and to test the concept that an anti-TNF antibody-drug-conjugate has the potential to provide superior efficacy than the traditional anti-TNF antibody in RA.

#### Secondary

3. To compare adalimumab with synthetic placebo control to establish assay sensitivity.
  4. To assess the pharmacokinetics (PK), pharmacodynamics, and immunogenicity of ABBV-3373.
  5. To assess the duration of the treatment effect of ABBV-3373 after discontinuation.
-

## 3.2 Primary Endpoint

---

The primary endpoint is the change in disease activity score (DAS)28 (C-reactive protein [CRP]) from Baseline (BL) at Week 12.

## 3.3 Secondary and Additional Endpoints

---

### Secondary Endpoints

1. Change in clinical disease activity index (CDAI) from BL at Week 12
2. Change in simplified disease activity index (SDAI) from BL at Week 12
3. Change in disease activity score (28 joints) (DAS28) erythrocyte sedimentation rate (ESR) from BL at Week 12
4. Achievement of low disease activity (LDA) (DAS28 [CRP]  $\leq 3.2$ ) at Week 12
5. Achievement of American College of Rheumatology (ACR) 50 at Week 12

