### Additional Endpoints

1. Change from BL in DAS28 (CRP) and DAS28 (ESR) at all visits
2. Change from BL in CDAI at all visits
3. Change from BL in SDAI at all visits
4. ACR20/50/70 response rates at all visits
5. Change from BL in individual components of ACR response at all visits
6. Achievement of LDA at all visits. Low disease activity is defined as DAS28 (CRP)  $\leq 3.2$ , DAS28(ESR)  $\leq 3.2$ , CDAI  $\leq 10$ , SDAI  $\leq 11$
7. Achievement of clinical remission at all visits. Clinical remission is defined as DAS28 (CRP)  $< 2.6$ , DAS28(ESR)  $< 2.6$ , CDAI  $\leq 2.8$ , SDAI  $\leq 3.3$
8. Change in Short Form-36 (SF-36) from BL at Week 12
9. Achievement of minimal clinically important difference (MCID) in change from BL in Health Assessment Questionnaire Disability Index (HAQ-DI) (defined as change from BL in Health Assessment Questionnaire  $\leq -0.22$ ) at all visits among subjects who have HAQ  $\geq 0.22$  at BL
10. Achievement of response (such as LDA) based on DAS28 (CRP), CDAI, or SDAI over time from Week 12 to Week 24 among subjects who have achieved DAS28 (CRP), CDAI, or SDAI response at Week 12

Additional endpoint definitions are provided in [Appendix D](#).

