## 5.8 Randomization/Drug Assignment

All subjects will be assigned a unique identification number by the IRT at the screening visit. For subjects who rescreen, the screening number assigned by the IRT at the initial screening visit should be used. The IRT will assign a randomization number that will encode the subject's treatment group assignment according to the randomization schedule generated by the statistics department at AbbVie.

Randomization will be stratified by factors listed in Section 4.1.

Forty-five subjects will be randomized to either the ABBV-3373 or adalimumab control arm according to a 2:1 ratio. Randomization will be stratified by the following factors:

- Stratification by current use of systemic GC ( $\leq 7.5$  mg/d prednisone equivalent) for treatment of RA at BL (yes/no).
- Stratification by prior exposure to non-anti-TNF biologics or targeted synthetic DMARDs (< 3 months and terminated not due to lack of efficacy or intolerance) (yes/no).

All AbbVie personnel with direct oversight of the conduct and management of the trial (with the exception of AbbVie Drug Supply Management Team), the investigator, study site personnel, and the subject will remain blinded to each subject's treatment throughout the study. To maintain the blind, the ABBV-3373 vials and matching placebo vials, as well as adalimumab PFS and matching placebo PFS, will be provided for the study. The IRT will provide access to unblinded subject treatment information in the case of a medical emergency. The procedure for breaking the blind is referenced in the IRT Training Slides provided to each study site.

AbbVie must be notified before the blind is broken unless identification of the study drug is required for medical emergency, i.e., situation in which the knowledge of the specific blinded treatment will affect the immediate management of the subject/patient's conditions (e.g., antidote is available). AbbVie must then be notified within 24 hours of the blind being broken. See [Appendix K](#) for contact information, including 24/7 AbbVie emergency contact coverage.

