### Primary Endpoint Analysis

Analysis of the primary endpoint will be conducted on the FAS based on treatment as randomized.

The primary endpoint is the change from BL in DAS28(CRP) at Week 12. The historical mean and standard deviation of the change from BL in DAS28(CRP) at Week 12 in adalimumab 80 mg eow are estimated to be  $-2.13$  and  $1.35$  respectively based on a meta-analysis of 3 historical adalimumab studies (Studies DE007, DE009, and DE011).

The first comparison in order to achieve the first primary objective of assessing the efficacy of ABBV-3373 is to compare change from BL in DAS28(CRP) at Week 12 in the ABBV-3373 group with  $-2.13$ , the adalimumab 80 mg eow historical mean change from BL at Week 12 based on the meta-analysis. The treatment mean change from BL and 90% confidence interval of ABBV-3373 will be estimated from Mixed Effect Model Repeated Measurements (MMRM) method including up to Week 12 data with treatment group, visits, treatment-by-visit interaction, BL values of the primary endpoint, and stratification factors with observed case (OC) data. The study will be declared positive if the comparison is significant and favoring ABBV-3373.

In order to achieve the second primary objective of comparing clinical efficacy of ABBV-3373 with adalimumab and to test the concept that an anti-TNF ADC has the potential to provide superior efficacy than the traditional anti-TNF antibody in RA, the second comparison is to compare ABBV-3373 with adalimumab for the primary efficacy endpoint with a Bayesian historical data borrowing approach. The same MMRM model as described in the first comparison will be used to estimate in-study mean and standard deviation. Informative normal prior for adalimumab will be determined based on historical adalimumab data and a non-informative prior will be used for ABBV-3373. The prior distributions and estimates from MMRM model will be combined to construct the posterior distributions which will be used for comparison between ABBV-3373 and adalimumab.

If the adalimumab group mean is not comparable with historical adalimumab data, for example, the confidence intervals of the mean based on historical and in-trial data don't overlap, the Bayesian approach based on historical data will not be performed, and the mean difference in change from BL in DAS28(CRP) at Week 12 between the ABBV-3373 group and adalimumab will be estimated only based on in-study data with the MMRM model described above.

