Historical data borrowing will only apply to the primary endpoint.

To address the secondary objectives of assay sensitivity, a synthetic placebo arm will be created with the propensity score matching approach using historical placebo subjects from similar trials with subject-level data. Details will be provided in the SAP.

## Secondary Endpoints and Additional Endpoints Analyses for BL to Week 12

For the first 12 weeks of treatment period, continuous efficacy variables will be analyzed using an MMRM method. Categorical efficacy variables will be analyzed using the Cochran-Mantel-Haenszel (CMH) test controlling for stratification variables. Non-responder imputation (NRI) will be used for primary inference purpose. Observed Case data will be summarized descriptively as a sensitivity analysis.

## Additional Endpoints Analyses up to Week 24

Statistical inference of additional continuous endpoints at each visit up to Week 24 will be conducted using analysis of covariance (ANCOVA) with treatment and stratification factors as the fixed factors and the corresponding BL value as the covariate. Additional categorical efficacy variables up to Week 24 will be analyzed using the same CMH test as for the binary secondary endpoint analysis.

Details on the analyses of the primary and other efficacy endpoints will be provided in the SAP.

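### Week 12 low disease activity is an absolute DAS28(CRP) cut-off tested without the baseline score: a valid test, but one that loses a little efficiency and moves with a chance baseline gap

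*Protocol*

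**What the plan says.** Protocol section 3.3 lists as secondary endpoint 4 "Achievement of low disease activity (LDA) (DAS28 [CRP" at or below 3.2 at Week 12). Among the additional endpoints are low disease activity on four indices and "Achievement of clinical remission at all visits", again defined by fixed values of DAS28(CRP), DAS28(ESR), CDAI and SDAI.

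Section 7.3 names the test for the period to Week 12: "Categorical efficacy variables will be analyzed using the Cochran-Mantel-Haenszel (CMH) test controlling for stratification variables". Missing responses are handled by a stated rule: "Non-responder imputation (NRI) will be used for primary inference purpose". The test is carried forward: "Additional categorical efficacy variables up to Week 24 will be analyzed using the same CMH test as for the binary secondary endpoint analysis".

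Section 5.8 gives the two stratification variables: "Stratification by current use of systemic GC" at baseline, and "Stratification by prior exposure to non-anti-TNF biologics or targeted synthetic DMARDs". Neither measures disease activity.

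The continuous analyses that the protocol spells out do use the starting score. The primary MMRM includes "BL values of the primary endpoint, and stratification factors with observed case (OC) data", and the ANCOVA for visits up to Week 24 takes the corresponding baseline value as covariate.

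**The concern.** A threshold on the level of a score, unlike a change or a percentage improvement, is easier to reach from a low start. The protocol lets starting scores vary widely. The DAS28(CRP) entry floor in section 5.1 is 3.2, the same value as the low disease activity cut-off, and it applies at Screening only. At the other end, a subject starting at 6.5 must fall by 6.5 − 3.2 = 3.3 points, more than the −2.982 that section 7.3 takes as the favourable case for ABBV-3373.

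Neither the randomisation nor the CMH controls the starting score, and the arms are 30 and 15. A chance gap therefore passes into the low disease activity comparison, while the baseline-adjusted primary analysis of the same score removes it. The two could then disagree for a reason unrelated to treatment. The protocol names this test, so it is not a detail left open for the SAP.

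**Working it through.** **Inputs from the protocol (section 7.3).** Arms of 30 and 15; mean change −2.13 on adalimumab and −2.769 to −2.982 on ABBV-3373; SD of change 1.35; one-sided 5%. The one-sided level is stated for the primary comparison; none is stated for low disease activity.

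**Assumptions not in the protocol.** Baseline DAS28(CRP) mean 5.3 or 5.8, and SD 0.8 or 1.0. Slope *s* of Week 12 score on baseline 0 to 0.9. Glucocorticoid use 40%, prior biologic or targeted synthetic DMARD 10%. No dropout; strata not prognostic.

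**Step 1: reproduce the plan's in-study power.** The protocol gives 43% to 63% for the continuous endpoint and no power for low disease activity. The standard error is 1.35 × √(1/30 + 1/15) = 1.35 × 0.316 = 0.427. The differences 0.639 and 0.852 give noncentralities of 1.50 and 2.00. A one-sided t-test on 43 df then has power 43.2% and 62.5%, so the plan's figures reproduce.

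**Step 2: the chance baseline gap.** Its SD is 0.316 × the baseline SD, i.e. 0.25 to 0.32 DAS28 points.

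**Step 3: dependence on the starting score.** Write B for baseline, m and b for its mean and SD. On adalimumab,

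P(LDA | B) = Φ{[3.2 − (B − 2.13 + (s − 1)(B − m))] / e}, with e = √(1.35² − (s − 1)²b²).

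- m = 5.8, b = 0.8, s = 0.3: e = 1.228. At B = 5.0 this is Φ((3.2 − 3.43)/1.228) = 0.43; at B = 6.6 it is Φ((3.2 − 3.91)/1.228) = 0.28.
- m = 5.3, b = 1.0, s = 0.9: e = 1.346. At B = 4.3 this is Φ((3.2 − 2.27)/1.346) = 0.76; at B = 6.3 it is Φ((3.2 − 4.07)/1.346) = 0.26.
- s = 0: no dependence on baseline.

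**Step 4: shift in the risk difference for a 1-SD gap.** This is approximately s × (density of the Week 12 score at 3.2) × (gap SD).

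- First setting: Week 12 mean 3.67, SD √(0.3² × 0.8² + 1.228²) = 1.252, density 0.297. Shift 0.3 × 0.297 × 0.253 = 0.023.
- Second setting: mean 3.17, SD √(0.9² × 1.0² + 1.346²) = 1.619, density 0.246. Shift 0.9 × 0.246 × 0.316 = 0.070.

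Simulation gives 2 to 7 percentage points over slopes 0.3 to 0.9. The standard error of the risk difference is √(p(1 − p) × 0.1), which is 0.158 at p = 0.5 and 0.149 at p = 0.33, so about 15 points.

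**Step 5: rejection with no true effect.** Simulation of the CMH over the four strata formed by both protocol factors, 30,000 trials per setting:

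- All trials: 4.7% to 5.2%.
- ABBV-3373 starting more than 1 SD of the gap lower: about 7% to 14%.
- ABBV-3373 starting more than 1 SD of the gap higher: about 1% to 3%.

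**Step 6: power at matched 5% one-sided size.** CMH → logistic model adding baseline, 20,000 trials per setting:

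| Slope | 30% more reduction | 40% more reduction |
|---|---|---|
| 0.3 | 34–38% → 34–38% | 49–54% → 50–55% |
| 0.6 | 29–31% → 31–32% | 42–44% → 45–46% |
| 0.9 | 24–27% → 27–30% | 35–39% → 40–43% |

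Within settings the gain is about 0–1, 1–3 and 2–5 points; at slope 0 it is nil.

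The unpenalised logistic score test ran at 5.6% to 6.2%, slightly above nominal. A Firth-penalised likelihood-ratio test, tried at baseline mean 5.4 and SD 0.9, held close to its nominal level. Power for the two effects went from 36% to 36% and 53% to 53% at slope 0.3, and from 29% to 31% and 41% to 44% at slope 0.6.

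**The case against.** The strongest reply is that nothing here is invalid. The CMH follows the stratified randomisation, needs no outcome model (an asset with 45 subjects) and keeps its size. The raised rejection rate after a favourable gap is balanced by the lowered rate after an unfavourable one, and any omitted prognostic variable behaves this way. A reader might infer that type I error is inflated; the calculations contradict that. This part of the reply stands in full.

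The size of the effect is also open. If change is taken as independent of baseline (slope 1), the protocol's figures give 73% reaching the cut-off from a start of 4.5 and 19% from 6.5, and a reader might conclude that baseline dominates. That assumes no regression to the mean. The protocol gives no slope, and at 0.3 the contrast between 1 SD below and 1 SD above the mean is only 43% against 28% in the first setting above.

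Third, the shift is well inside the noise. Low power for this endpoint comes mainly from 45 subjects and from dichotomising, which adjustment does not cure.

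Last, section 7.3 ties a positive or successful study to DAS28(CRP) change alone, and leaves further detail to the SAP, which may hold a supportive adjusted analysis.

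What remains is narrower. The protocol fixes an unadjusted test for a named secondary endpoint while adjusting the same score elsewhere. The trial is run once, with whatever gap it draws, and adjustment chosen after seeing that gap would be post hoc.

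**Conclusion.** The point holds as one of efficiency and of conditional shift, not of bias or error control. Over slopes 0.3 to 0.9 and baseline SD 0.8 to 1.0, a 1-SD chance gap moves the Week 12 low disease activity difference by about 2 to 7 percentage points against a standard error near 15. Omitting baseline costs about 0 to 5 points of power. All of this rests on assumed baseline values and on a slope that the protocol does not state.

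The protocol does not support a reading that the CMH is wrong for every binary endpoint. ACR50 is already defined relative to baseline, and remission may have too few events for a model. The priority is minor, because low disease activity does not determine study success.

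**What to change.** In section 7.3, pre-specify for low disease activity at Week 12 a Firth-penalised logistic model with treatment, the two stratification factors and continuous baseline DAS28(CRP). Test treatment with the penalised likelihood-ratio test, not the plain score test. Leave non-responder imputation as it is, and report a standardised risk difference with its confidence interval.

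Keep the CMH as a supportive analysis of this endpoint and as the test for ACR50. Apply the same model to the other low disease activity and remission cut-offs, using the baseline of the same index, only where event counts allow.

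The cost is a short change to section 7.3 with matching SAP text. No new data are needed, since the baseline scores are already required for the continuous analyses. The downside is that the result becomes model-based, for a modest gain.
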